self-regulation and medical regimen adherence. We will examine each relationship separately prior to examining the full mechanistic model. To examine whether context is associated with level of momentary self-regulation, we will fit several multilevel models with momentary context as a predictor of momentary self-regulation measure. In Aim 2, we have identified several challenging contexts associated with worse momentary self-regulation, and we will confirm these relationships in this treatment-seeking sample of participants. The multilevel models will include a random individual-level effect to account for the non-independence of repeated observations over the 28-day period within an individual. Additionally, the models will also include a fixed effect of time to account for changes in momentary self-regulation over the treatment period. We will also consider a random individual-level slope term if there is significant variability in this change over time between individuals. Such a change in self-regulation over time may be due to the cumulative effect of Laddr use over the treatment period. We will also test whether including an interaction between context and recent Laddr usage is significant indicating Laddr use affects the association between context and momentary self-regulation. These models will identify contextual factors associated with increased or decreased momentary self-regulation.

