The next model will examine the relationship between level of momentary self-regulation and daily medical regimen adherence. One model for each subscale of the momentary self-regulation will be fit. In each model, momentary self-regulation will be the predictor and daily medical regimen adherence (smoking abstinence for smokers and daily physical activity for overweight/obese participants with binge eating disorder) will be the outcome. These models will identify the influence of momentary self-regulation on medical regimen adherence. Together with the previous set of models, the components of a mechanistic effect of momentary self-regulation on medical regimen adherence will be estimated. If each relationship is significant, we will fit a full multi-level structural equation model to examine the indirect effect of momentary context on medical regimen adherence as well as the direct effect of context on medical regimen adherence, independent of momentary self-regulation. Bootstrapping will be used in estimating the indirect effect in the mediation model. Bootstrapping involves taking numerous pseudo-replicate samples from the dataset and using the variability in the statistic from sample to sample to construct an interval estimate conveying the direction, magnitude, and precision

of an indirect effect. This mediation model will allow us to estimate the impact of self-regulation as a mechanism for decreased medical regimen adherence in challenging contexts.

At the individual level, we wish to examine whether Laddr can influence momentary self-regulation in a positive direction and, in turn, increase medical regimen adherence. To test this hypothesis, we will examine both the effect of time in the study on momentary self-regulation via multilevel models (e.g. linear mixed-effects models) as well as the effect of various Laddr engagement metrics on momentary self-regulation. Since Laddr use is offered as an intervention during the 28-day intervention period, time in study serves as a proxy for the cumulative effect of Laddr use. Since individuals will differ in their use of Laddr during the course of the intervention period, we will also examine Laddr engagement metrics (e.g., guides read, goals tracked) in addition to time. If Laddr usage appears to influence momentary self-regulation in a positive direction, we will again fit a multi-level structural equation model to examine both the indirect and direct effects of Laddr use on medical regimen adherence.

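### The models of self-regulation on adherence state no time term, so a trend shared over the 28 days can be read as a momentary influence

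*Combined protocol and SAP*

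**What the plan says.** All of this stands in the Statistical Analysis Plan section of the combined document.

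- **Context on self-regulation.** "The multilevel models will include a random individual-level effect to account for the non-independence of repeated observations". In addition, "the models will also include a fixed effect of time to account for changes in momentary self-regulation over the treatment period". A random slope is conditional: "We will also consider a random individual-level slope term if there is significant variability in this change over time between individuals".
- **Self-regulation on adherence.** The plan moves on: "The next model will examine the relationship between level of momentary self-regulation and daily medical regimen adherence". One model is fitted per subscale, specified as "In each model, momentary self-regulation will be the predictor and daily medical regimen adherence" the outcome (abstinence in smokers, physical activity in the binge eating sample). No time term or random effect is named here. The stated reading is that "These models will identify the influence of momentary self-regulation on medical regimen adherence".
- **Gate.** "If each relationship is significant, we will fit a full multi-level structural equation model". No time term is stated for that model either.
- **Laddr analysis.** Time returns as an exposure: "time in study serves as a proxy for the cumulative effect of Laddr use".

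**The concern.** Under Study Design, both series are meant to move over the same 28 days. Laddr activities are expected to improve self-regulation. Smokers aim to be abstinent by study end, and binge eating participants are encouraged to raise their activity goals week by week. By the plan's own account time stands for cumulative Laddr exposure, so it is a possible common cause of predictor and outcome.

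If both series rise, days late in the study have high self-regulation and high adherence even when a good day for one is not a good day for the other. A model with a person intercept but no time term attributes this to momentary self-regulation. The reason given for time in the context models does not transfer directly, because self-regulation is now the predictor. Two analysts following the text could fit different models.

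Two things are at stake: the claim about influence, and one of the two significance conditions for the mediation model. The other condition, context on self-regulation, is already time-adjusted.

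**Working it through.** **1. The plan's own figures (Power and Sample Size Justification).** 77 × 4 × 28 = 8,624, and 8,624 × 0.90 × 0.75 = 5,821; both reproduce. With two-sided 5% assumed, the detectable context effect is 2.80 × √[(1 − ICC)/(N p(1 − p))]:

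- ICC 0.3, prevalence p = 0.10: 2.80 × √[0.7/(5,821 × 0.09)] = 0.102 SD.
- ICC 0.6, p = 0.30: 2.80 × √[0.4/(5,821 × 0.21)] = 0.051 SD.

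This matches the stated 0.05–0.10 SD. It covers context on self-regulation only; no power figure is given for self-regulation on adherence.

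**2. Inputs for the check.**

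- From the documents: 28 days, 75% response (taken as 21 days per person), 50 people (the target) or 69 (77 less 10%).
- Assumed: ICC 0.5 for both variables (the plan gives 0.3–0.6 for its context calculation), linear drift common to everyone, one self-regulation value per day, no true same-day link.
- Drift dx (self-regulation) and dy (adherence) is in total SD over the 28 days. The documents give none, so a range is shown.

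**3. Formula, person intercept but no time term.** The variance of day scaled 0 to 1 is v = (28² − 1)/(12 × 27²) = 0.0895. Per person:

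- Sxx = 20 × 0.5 + 21 v dx²
- Sxy = 21 v dx dy
- spurious slope b = Sxy/Sxx
- s² = (20 × 0.5 + 21 v dy² − b Sxy)/20
- SE = √[s²/(n Sxx)]
- rejection = P(Z > 1.96 − b/SE) + P(Z < −1.96 − b/SE)

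Example, n = 50, drift 0.5/0.5: Sxy = 21 × 0.0895 × 0.25 = 0.470; Sxx = 10.470; b = 0.045; s² = 0.522; SE = √[0.522/523.5] = 0.0316; b/SE = 1.42; rejection 29.5%.

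| Drift dx/dy | n | b | SE | Rejection, formula | Simulation, no time | Simulation, with day |
|---|---|---|---|---|---|---|
| 0.5/0 | 50 | 0 | 0.031 | 5.0% | 5.3% | 5.0% |
| 0.2/0.2 | 50 | 0.007 | 0.032 | 5.6% | 4–6.5% across runs | about 5% |
| 0.25/0.5 | 50 | 0.023 | 0.032 | 11% | 9.5–11.3% | about 5% |
| 0.5/0.5 | 50 | 0.045 | 0.032 | 30% | 29–30% | about 5% |
| 0.5/0.5 | 69 | 0.045 | 0.027 | 39% | 38–38.5% | about 5% |

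**4. Sensitivity to choices that the plan leaves open.**

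- *Prompts averaged by day.* Averaging shrinks noise in self-regulation but not its trend. At ICC 0.45 and 0.5/0.5 drift, rejection is 67% (n = 50) and 79% (n = 69) without time, and about 5% with it. A random-intercept mixed-model fit at n = 69 (100 runs) gave 78% and 7%. Averaging assumes independent prompt errors within a day; correlated errors would fall in between.
- *Drift in within-person SD.* With n = 50: 5.9% at 0.25/0.5 and 11.5% at 0.5/0.5.
- *Abstinence rising from 5% to 20% of days (n = 50).* 9.7% at self-regulation drift 0.25 and 20.2% at 0.5; 5.9% with day.

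**5. The gate.** With a real context effect of 0.10 SD and n = 50, both tests are significant in 9.5% (0.25/0.5) and 25.1% (0.5/0.5) of runs without time in the second model, and in 4.4% with it.

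**The case against.** **Carry-over.** The section introduces one family of multilevel models for both relationships, and its general wording on the random effect and time can fairly be read as covering all of them. This stands: the text is an unstated specification. A reader might infer that the sponsor plans to leave time out; the documents do not show that.

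**Estimand.** The section opens by asking whether changing self-regulation goes with changing adherence, and for that purpose joint trend is partly signal. This also stands. It matters most if people have their own slopes and these are correlated. With 69 people, slope SD 0.5 and correlation 0.5, a fixed day term alone still rejects in 14.2% of runs; adding a random slope in adherence gives 6.9%, and removing each person's own trend from self-regulation gives 5.1%. A reader might infer that random slopes and detrending must be mandatory. The documents do not support that: those rejections are errors only for the same-day claim, and the slope SD and correlation are assumed. Neither remedy was tested for abstinence or for people who answer as few as 12 of 112 prompts, whom Sample Size counts.

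**Consequence.** Passing the gate only leads to fitting the structural equation model, which then reports an interval. A spurious slope of 0.045 times a context effect of 0.10 SD is an indirect effect of 0.0045 SD. A reader might take the gate rates as rates of false mediation conclusions; they are not.

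What remains is that the momentary claim and the gate rest on models whose time adjustment is not stated, in a design meant to create shared trend.

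**Conclusion.** The concern holds as a gap in specification with a real, conditional consequence. For the claim about the level of momentary self-regulation, shared trend is confounding, and nothing stated for these models or for the context structural equation model removes it.

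The size cannot be fixed from the documents. Inflation is negligible if only one series drifts or both drift about 0.2 SD. It is about 10% at 0.25/0.5 SD and about 30% at 0.5/0.5 SD, against about 5% with a day term. These figures assume 50 people, ICC 0.5, drift common to everyone, one self-regulation value per day and a two-sided 5% test. Averaging prompts by day raises them; measuring drift in within-person SD lowers them. The direction is firm and the percentages are illustrative. No stated sample size or power figure changes. The point should be settled before analysis.

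**What to change.** State in the Statistical Analysis Plan:

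1. The models of self-regulation on adherence, and both equations of the context structural equation model, include a random individual effect and a fixed effect of day in study.
2. The conditional random slope already described for the context models also applies to day in the adherence equation.
3. The time-adjusted coefficient supports the momentary claim and decides the gate. The unadjusted coefficient is reported beside it as a description of joint change over the 28 days, which serves the section's opening purpose.
4. Day is not adjusted for where time is itself the Laddr exposure.

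Entering self-regulation as the deviation from the person's own trend is an optional sensitivity analysis for correlated person-specific slopes.

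**Cost.** A few sentences; day in study is known for every record. At 0.5 SD drift and ICC 0.5, day explains R² = (0.25/12)/(0.25/12 + 0.5) = 0.04 of the within-person variance in self-regulation, so the standard error rises by 1/√0.96 = 1.02, about 2%. Adjustment may also absorb part of a slow Laddr-driven effect, which is why the unadjusted coefficient stays in the report. If carry-over was always intended, the change only writes it down.

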We propose the sample sizes above to reach 50 participants in each sample with at least 10% EMA response percentage over the duration of the four-week study (at least 12/112 EMAs). We calculated the percentage of participants who completed at least 10% of their EMAs in Aim 2 at Dartmouth. We then estimated a target sample size to reach at least 50 participants in each sample with adequate EMA participation (at least 10% completion). The proposed sample sizes account for participants who sign consent but participate minimally, and the target sample sizes of 50 for each sample with at least 10% EMA completion were determined through power calculations in Aim 2.

Statistical Analysis Plan

To evaluate the degree to which changing self-regulation is associated with changes in medical regimen adherence (measured as daily smoking abstinence in smokers and daily physical activity in overweight/obese individuals with binge eating behavior), we will fit several multilevel models (e.g., linear mixed-effects models) in addition to an overall model examining mechanistic effects. Details are provided in the following text. At the momentary level, there two relationships to be examined to understand the role of self-regulation in behavior change: the relationship between context and self-regulation, and the relationship between

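### The mediation models are fitted only after a screen on the same data, so reported indirect effects are selectively estimated and a failed screen leaves mediation unbounded

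*Combined protocol and SAP*

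**What the plan says.** All of this is in the Statistical Analysis Plan section of the combined document.

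- The section states its purpose as "To evaluate the degree to which changing self-regulation is associated with changes in medical regimen adherence". It promises multilevel models "in addition to an overall model examining mechanistic effects", with no condition on that overall model.
- It then sets an order: "We will examine each relationship separately prior to examining the full mechanistic model".
- Both component models, context to self-regulation and self-regulation to adherence, are fitted whatever they show: "the components of a mechanistic effect of momentary self-regulation on medical regimen adherence will be estimated".
- The context mediation model is conditional: "If each relationship is significant, we will fit a full multi-level structural equation model". The indirect effect, the direct effect of context and the bootstrap interval belong to that model only.
- The Laddr mediation model has a different condition: "If Laddr usage appears to influence momentary self-regulation in a positive direction, we will again fit a multi-level structural equation model". It concerns one path and one direction, and no criterion is given for when the influence counts as apparent.

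The plan gives no significance level, no multiplicity rule across contexts and subscales, and no report to be made when a screen fails.

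**The concern.** An estimate reported only when its components have reached significance in the same data is, on average, too far from zero. The planned bootstrap interval takes no account of that selection. When the screen fails, no indirect or direct effect is planned, so a trial with weak or negative findings cannot say how large a mediated effect it has excluded. For Laddr, an unfavourable first path is never carried through to adherence. The opening of the section reads as if the mechanistic model will always be reported; the later text makes it conditional.

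Two features make the context screen less clean than it looks. The model that tests self-regulation against adherence is described with self-regulation as the predictor and does not mention context, so the path screened need not be the path inside the mediation model. The screen is also repeated over several contexts and over each self-regulation subscale.

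**Working it through.** **Inputs from Sample Size and from Power and Sample Size Justification.** 77 participants per sample, 4 prompts a day, 28 days; 10% drop-out; 75% EMA completion; a target of 50 per sample with adequate EMA data; an individual-level mediation benchmark of 80% power at n = 71 with .39 on each path; at least 80% power for context differences of 0.05–0.10 SD in self-regulation. No power is given for self-regulation to adherence. **Assumed:** two-sided 0.05 at the screen, no direct effect.

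**Step 1: the plan's own figures.** 77 × 4 × 28 = 8,624, and 8,624 × 0.90 × 0.75 = 5,821.2; both agree with the plan. For the benchmark, simulate M = aX + e and Y = bM + e with a = b = .39, unit residual variances and n = 71. Power is 0.780 with a percentile bootstrap (Monte Carlo SE 0.01), 0.856 with a bias-corrected bootstrap and 0.779 for joint significance. These bracket the stated 80%.

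**Step 2: the two-path screen on that benchmark.** Inflation = mean(â·b̂ given that the screen is passed) ÷ (a·b), with a·b = .39² = 0.1521 (60,000 datasets per row). The first value in each range tests b without adjusting for X, as the SAP describes; the second adjusts for X.

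| n | Model fitted | Inflation ratio |
|---|---|---|
| 50 (target) | 61% / 55% | 1.28 / 1.34 |
| 69 (77 × 0.90 = 69.3) | 80% / 76% | 1.13 / 1.15 |
| 71 (benchmark) | 82% / 78% | 1.11 / 1.14 |
| 77 | 86% / 82% | 1.09 / 1.11 |

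A repeat run put the upper end at n = 50 at about 1.35. At n = 71 the mean reported effect is 1.11 × 0.1521 = 0.169 to 1.14 × 0.1521 = 0.173. Without the screen the mean ratio is 0.99 to 1.00 in these rows. With .59 on each path and n = 71 the ratio is 1.00–1.01.

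**Step 3: dependence on power.** For one path with Z ~ N(δ, 1) and power P, the ratio after selection is 1 + [φ(1.96 − δ) − φ(1.96 + δ)] ÷ (P·δ).
- 80% power: δ = 2.802, ratio 1 + 0.280 ÷ (0.80 × 2.802) = 1.125. For two such independent paths, 1.125² = 1.27.
- 50% power: δ = 1.960, ratio 1.407. One path at 80% and the other at 50%: 1.125 × 1.407 = 1.58.
- 95% on both paths: 1.06. 99% on both: 1.01.

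**Step 4: repeated measures, where the context screen acts.** Assumptions: continuous variables, within-person estimation with cluster-robust standard errors, 28 usable days, slope SD 0 or 0.2.
- .26 per path: the screen opens in 99.9–100% of trials and the ratio is 0.99–1.00, at n = 50 and n = 69.
- .10 per path: inflation about 1–22% at n = 69 and 7–45% at n = 50.
- .05 per path: about two- to four-fold.

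With only 14 usable days, n = 50 and .10 per path, inflation reached 84%.

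**Step 5: a true null.** With a = .39, b = 0 and n = 71, the screen is passed in about 4% of datasets and the conditional mean indirect effect is about zero.

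The Laddr screen was not simulated.

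**The case against.** The strongest case against is that the screen rarely bites. The context paths are tested on thousands of momentary observations, and with moderate within-person effects the model would almost always be fitted, with no visible bias. The stated question about the association of self-regulation with adherence is also addressed by a component model that has no condition. Both points stand. What remains is that power for the adherence path is unknown, that a daily binary abstinence outcome carries less information than the continuous one simulated, and that the bias returns for small effects.

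A reader might infer more than the documents support:

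- **That a null result gives no estimate of the mechanism.** Both component paths are estimated regardless. What is lost is the indirect effect, the direct effect and their interval.
- **That a mechanism is reported only when it looks positive.** The context condition is significance, in either direction. Only the Laddr condition is directional.
- **That the screen creates false mediation.** Step 5 shows no excess in a single test. Interval coverage after selection is also secondary: it stayed at 94–98% for .39 and .26 in individual-level runs and fell to about 78% only at .14.
- **That individual-level inflation at effects below the benchmark describes the context screen.** That screen acts on repeated measures, where the bias at .26 is near nil.
- **That covariance between person-specific slopes could produce mediation that the screen misses.** The only random slope the SAP contemplates is for change over time, so this has no basis in the stated models.

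**Conclusion.** The point holds as one of selective estimation and incomplete reporting. Both mediation models are conditional, the opening of the section is not, and there is no fallback. Indirect effects that survive the context screen are biased away from zero unless both paths are highly powered, and a failed screen leaves the mediated effect without an estimate or interval.

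The size can only be ranged: about 11–14% (n = 71) to 28–35% (n = 50) on the plan's individual-level benchmark; in repeated measures, from near nil at .26 per path to roughly 1–45% at .10, and more below that. These ranges rest on a two-sided 0.05 screen, continuous variables, no direct effect in the individual-level runs and 28 usable days in the repeated-measures runs. No figure is offered for the Laddr screen; the objection to it rests on its wording.

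**What to change.** Delete both conditions, "If each relationship is significant" and "If Laddr usage appears to influence momentary self-regulation in a positive direction". Fit the mediation model for every context, self-regulation subscale and Laddr metric examined in the component models, whatever those models show. Report all indirect and direct effects with bootstrap intervals. Keep joint significance of the two paths as a label on the results, not as a condition for fitting. This also brings the later text into line with the unconditional overall model announced at the start of the section.

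The cost is a change of wording and additional model fits, with no new data or participants. Some reported intervals will include zero.

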
Additionally, we will evaluate whether Laddr influences task behavior in our four tasks as well as fMRI activity and connectivity by comparing the pre and post scan results.

[Power and Sample Size Justification](#)

With 77 participants in each sample with up to 4 EMA responses per day for 28 days, the maximum number of observations in the momentary dataset is 8,624. However, EMA response rates are not expected to be 100%, and some participants may withdraw from the study. With 10% study drop-out and 75% EMA completion rate, the number of observations in a momentary dataset may be closer to 5,821. Even with this sample size, there will be adequate power to detect momentary relationships between contextual factors and momentary self-regulation. For example, with intraclass correlations ranging from 0.3 to 0.6, and prevalence of contexts of interest (e.g., recent exposure to smoking cue, easy food access) between 10% and 30%, there would be at least 80% power to detect differences in momentary self-regulation measures between context between 0.05-0.10 times an SD. These are small effect sizes. In the pilot data, the average SD of a momentary self-regulation measure was between 0.5 and 0.9, and the stated standardized effect sizes are equivalent to detectable mean differences

between contexts of 0.03-0.09 points on the momentary self-regulation subscales, which range from 1 to 5. Well-developed formulae for determining power to detect indirect effects within a multilevel structural equation model of intensively collected data do not exist. However, simulation studies of the bootstrap approach at the individual-level indicate that with a sample size of 71, an indirect effect with medium-sized component effects ($\beta = .39$) can be detected with 80% power.¹

¹Fritz MS, [name] DP. Required sample size to detect the mediated effect. *Psychol Sci* 2007. Mar; 18(3):233-239.

Protection of Human Participants

Potential Risks:

The potential risks associated with the data collected are low.

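### Time in study and the pre/post scan comparison are read as Laddr effects, but without a comparator neither can separate Laddr from other change over the 28 days

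*Combined protocol and SAP*

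**What the plan says.** The Statistical Analysis Plan section asks, at the individual level, whether Laddr can improve momentary self-regulation and through it adherence. One of the two tests it names is the effect of time in the multilevel models, because "time in study serves as a proxy for the cumulative effect of Laddr use". The other uses observed use: "we will also examine Laddr engagement metrics (e.g., guides read, goals tracked) in addition to time".

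Earlier in the same section, in the context models, "the models will also include a fixed effect of time". The SAP remarks there that a change over time might reflect cumulative Laddr use, and adds: "We will also test whether including an interaction between context and recent Laddr usage is significant".

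The mediation step is conditional: "If Laddr usage appears to influence momentary self-regulation in a positive direction, we will again fit a multi-level structural equation model".

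For the scans, the question the SAP sets is "whether Laddr influences task behavior in our four tasks as well as fMRI activity and connectivity by comparing the pre and post scan results".

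Under Study Design, all participants are asked to answer EMAs and use Laddr for the same 28 days. The two samples are two populations, not two arms. No control group, waitlist or Laddr-free run-in is described.

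**The concern.** Both analyses are offered as answers to a causal question about Laddr. In both, exposure to Laddr is the same thing as elapsed time in the study, so anything else that changes over those 28 days enters the estimate. The protocol itself supplies several candidates:

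- Nicotine replacement is allowed in the smoking sample and tracked by participant (Study Design), but it appears in no model.
- EMA non-response is expected, and persistently poor compliers may be withdrawn and an additional participant enrolled (Data Monitoring).
- The same tasks are given at baseline and follow-up (Study Assessments).
- Fatigue is a listed risk of the testing (Potential Risks), and four prompts a day may themselves alter ratings.

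Goal tracking is not on this list, because it is part of Laddr.

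Study Design says the study will assess Laddr's effect on self-regulatory targets. On these two analyses, upward drift from other causes could be reported as that effect, and downward drift, for example from survey fatigue, could hide a benefit.

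**Working it through.** **1. The plan's own figures.** 77 × 4 × 28 = 8,624 prompts, and 8,624 × 0.90 × 0.75 = 5,821. This agrees with the Power and Sample Size Justification: "With 10% study drop-out and 75% EMA completion rate, the number of observations in a momentary dataset may be closer to 5,821". It corresponds to 77 × 0.90 = 69.3 people with 5,821 / 69.3 = 84 EMAs each. No power figure is given for a time or Laddr effect.

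**2. How often would drift with no Laddr effect be significant?** Inputs from the plan are 69.3 people, 84 EMAs each and ICC 0.3–0.6. Assumed inputs are a total upward drift of 0.10 SD over 28 days (0.05–0.09 points at the stated SDs of 0.5–0.9), a between-person slope SD of 0–0.4, and two-sided alpha 0.05.

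SE² = (slopeSD² + (1 − ICC)/(m·v))/n, where v = 0.0895 is the variance of 28 equally spaced days scaled to 0–1. P(significant and positive) = 1 − Φ(1.96 − 0.10/SE).

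Example with ICC 0.3 and slope SD 0: 0.7/(84 × 0.0895) = 0.0931; √(0.0931/69.3) = 0.0367; P = 78%.

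| Data | ICC | Slope SD | SE | P |
|---|---|---|---|---|
| n = 69.3, m = 84 | 0.3 | 0 | 0.0367 | 78% |
| | 0.3 | 0.4 | 0.0604 | 38% |
| | 0.6 | 0 | 0.0277 | 95% |
| | 0.6 | 0.4 | 0.0555 | 44% |
| n = 50, m = 12 | 0.3 | 0 | 0.1142 | 14% |
| | 0.3 | 0.4 | 0.1274 | 12% |
| | 0.6 | 0 | 0.0863 | 21% |
| | 0.6 | 0.4 | 0.1032 | 16% |

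The lower block is the Sample Size floor ("at least 12/112 EMAs" for 50 people). Its figures are lower only because there are fewer data. A random slope does not help either: it describes spread around the mean trend, not the cause of the trend.

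**3. Could apparent drift arise with no true change?** Assume completion falls linearly over the 28 days, averaging the plan's 75%, and that the odds of answering are 1.65 times higher per within-person SD of self-regulation (log-odds 0.5). Solve the intercept each day for that day's completion, take the mean within-person z among answered prompts, fit its completion-weighted slope over 0–1, and multiply by √(1 − ICC).

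- Completion from 90% to 60%: the mean z of answered prompts rises from 0.049 to 0.189; slope 0.140; apparent drift 0.140 × √0.4 to 0.140 × √0.7 = 0.09–0.12 SD.
- Completion from 85% to 65%: slope 0.093; apparent drift 0.06–0.08 SD.

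Because answering here depends on the current, unrecorded rating, a standard mixed model does not remove this drift.

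**4. Pre/post.** Assume a practice shift of 0.2 SD of the paired difference and no Laddr effect. The paired t test (noncentral t, upper tail, two-sided alpha 0.05) is significant in 37% of comparisons at n = 69 and 28% at n = 50.

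**5. Does the usage analysis settle the question?** It is not aliased with time, but use is self-directed. In simulation with zero Laddr effect, use was allowed to follow same-day self-regulation (an assumed 0.5–1 logit per SD; 69 people, 75% completion, ICC 0.3–0.6). Prior-day use was falsely positive in 22–100% of runs, and still in 9–77% after adjusting for the prior day's mean rating.

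**The case against.** The plan is more guarded than the proxy sentence suggests. The context paragraph only says that change over time might reflect Laddr, and the opening of the SAP speaks of association. Engagement metrics are added because participants will differ in use, and the mediation condition names usage, not time. Both scan visits include practice outside the scanner, which may reduce practice effects, and some tasks, such as movie-watching, are not obviously sensitive to practice. A single-group mechanism study is also a legitimate design.

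Most of this stands, but it does not rescue the two analyses. The hedge names no other cause, and the later paragraphs use time and pre/post change to decide whether Laddr has an influence. Pre-scan practice reduces carry-over between visits but does not exclude it. The mediation condition is a matter of clarification: the SAP equates time with cumulative use, so it should say that a time trend does not satisfy the condition.

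It is also fair to object that the drift, non-response and practice sizes are assumed. They are. The documents give only mean completion, and the non-response result needs a substantial fall in completion together with selective answering in the favourable direction.

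**Conclusion.** The point holds for the time effect and the pre/post comparison. It is a problem of identification, not of power: more participants make a non-Laddr drift more likely to reach significance. Under an assumed 0.10 SD drift and no Laddr effect, the chance of a significant positive time effect is 38–95% at the planned data volume and 12–21% at the floor. Under assumed selective non-response, apparent drift of about 0.06–0.12 SD could arise with no true change. The documents do not show that such drift will occur.

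A reader might infer three stronger conclusions that the documents do not support:

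- *That every Laddr analysis is confounded with time.* The engagement analysis is run in addition to time, and the context-by-usage interaction sits in models with a time term. Their weakness is self-selected use.
- *That the plan lets a time trend trigger mediation.* The stated condition is usage; the wording is ambiguous, not wrong.
- *That a control arm is required.* The data remain usable for the mechanistic aims. What needs to change is the attribution to Laddr.

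**What to change.** In the SAP:

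1. Delete the proxy sentence.
2. Report the time and pre/post results as uncontrolled change during the study, not as a Laddr effect.
3. State that a time trend alone does not open the Laddr mediation model, and that this step depends on the usage analysis with day in study in the model.
4. In that analysis, measure engagement before the prompt and separate its within-person and between-person parts.
5. Report usage and mediation results as associations, because use can follow from self-regulation.
6. Treat adjustment for the prior rating, and a check on next-day engagement, as sensitivity analyses only. Fit the check jointly with prior-day use. In simulations with a real prior-day effect and use that persists from day to day, the check alone was positive in 7–32% of runs, against 1–4% when fitted jointly. State that neither analysis removes reverse causation, and that prior-day use addresses a short-term effect, not a cumulative one.
7. Describe nicotine replacement as a limitation, or adjust for it if dates of use are recorded.

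No new data collection is needed. The costs are a narrower claim, the loss of any attribution to Laddr of a slow benefit shared by all users, and extra analyses for each subscale, engagement metric and sample. Prior-rating adjustment also loses data when response is sparse. At 12 of 112 EMAs spread evenly, (1 − 12/112)⁴ = 0.64 of ratings have no rating on the previous day.
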